**List of Abbreviations (continued)**

QRS (interval)	The interval between the Q wave and the S wave in the heart's electrical cycle as measured by electrocardiogram; principal deflection in the electrocardiogram
QT (interval)	A measure of the time between the start of the Q wave and the end of the T wave in the heart's electrical cycle as measured by electrocardiogram
QTc (interval)	A measure of time between the start of the Q wave and the end of the T wave in the heart's electrical cycle measured by electrocardiogram corrected for heart rate
SAD	Single Ascending Dose
SAE	Serious Adverse Event/Serious Adverse Experience
SAP	Statistical Analysis Plan
SC	Subcutaneous
SD	Standard Deviation
SDTM	Study Day Tabulation Model
SOC	System Organ Classes
$t_{1/2}$	Terminal phase half-life
TFL	Tables, Figures, and Listings
T max	Time to reach maximum measured plasma concentration
VS	Vital Sign
V z /F	Volume of distribution
WBC	White Blood Cell

## 1. PREFACE

The Analysis Plan for “A Phase 1, Three-Part, Randomized, Double-Blind, Single and Multiple Subcutaneous Dose Escalation Study to Determine the Safety, Tolerability, and Pharmacokinetics of Rezafungin in Healthy Adult Subjects” (DMID Protocol 17-0088) describes and expands upon the statistical information presented in the protocol.

The sponsor terminated the study on 27APR2020 due to safety concerns. No subjects were enrolled into Single Ascending Dose (SAD) Cohort 3 (30 mg) and above, any Multiple Ascending Dose (MAD) cohort, or the Bioavailability (BA) cohort. Accordingly, this SAP describes analyses of data from subjects in SAD Cohort 1 (1 mg) and Cohort 2 (10 mg) only.

Due to early termination of the study, the sponsor confirmed an abbreviated clinical study report (CSR) will be provided. The statistical analysis plan noted in the protocol was not drafted and approved prior to study closure and was therefore deemed by the sponsor as not required. This document includes sufficient description of analyses, definitions, tables, figures, and listings (TFLs) for programming of the abbreviated CSR. Within the TFL mock-ups (Appendices 1, 2, and 3), references to abbreviated CSR sections are included. Any deviation from this SAP in the statistical analysis will be described and justified in the abbreviated CSR.

---

## **2. INTRODUCTION**

### **2.1. Purpose of the Analyses**

These analyses will assess the safety of single 1 mg or 10 mg subcutaneous doses of rezafungin given subcutaneously and pharmacokinetics (PK) of a single 10 mg subcutaneous dose.

### **3. STUDY OBJECTIVES AND ENDPOINTS**

#### **3.1. Study Objectives**

Refer to Protocol v6.0.

#### **3.2. Endpoints**

Refer to Protocol v6.0.

#### **3.3. Study Definitions and Derived Variables**

##### **3.3.1. Dose Group**

Dose Group defines a grouping of subjects used for statistical analysis, where subjects within a Dose Group received the same dose and dosing schedule under the same fasting status. Note that for data from a subject to be analyzed as part of their Dose Group, the subject must also qualify for inclusion into the respective analysis population (As described in Section 5.3) for that data. Definitions for each Dose Group to be analyzed in the report, and their ordering, are provided in the list below.

- SAD Any Dose: Subjects from SAD cohorts who receive any dose of rezafungin.
- SAD 1 mg: SAD, Cohort 1 subjects receiving 1 mg of active drug.
- SAD 10 mg: SAD, Cohort 2 subjects receiving 10 mg of active drug.
- Placebo: SAD subjects receiving placebo.

The “SAD Any Dose” Dose Group will be included in analyses of safety endpoints only.

##### **3.3.2. Baseline**

For clinical laboratory results, and vital sign (VS) measurements, the baseline assessment is the last measurement recorded prior to dosing, except for height, weight, and BMI, which baseline will be defined as the measurements recorded at the initial Screening Visit. For electrocardiogram (ECG) results, baseline is defined as the median of the triplicate measurements taken within 60 minutes of dosing. If multiple triplicate measurements are taken prior to dosing, the median of last set of triplicates will be used as baseline.

Age will be based on age at enrollment. Age at enrollment is an integer value with units of years and is calculated from the subject’s enrollment date (ENROLLDT) and birth date (BRTHDT) using the following algorithm.

- If month(ENROLLDT) > month(BRTHDT), then AGE = year(ENROLLDT) – year(BRTHDT)
- If month(ENROLLDT) < month(BRTHDT), then AGE = year(ENROLLDT) – year(BRTHDT) – 1
- If month(ENROLLDT) = month(BRTHDT) and day(ENROLLDT) ≥ day(BRTHDT), then AGE = year(ENROLLDT) – year(BRTHDT)
- If month(ENROLLDT) = month(BRTHDT) and day(ENROLLDT) < day(BRTHDT), then AGE = year(ENROLLDT) – year(BRTHDT) – 1

### **3.3.3. Study Day**

The day that the subject received study product is considered Study Day 1 for each subject. The day prior to dosing is considered Study Day = -1, not Study Day = 0.

#### **4. SAMPLE SIZE CONSIDERATIONS**

No formal sample-size calculations based on testing a statistical hypothesis were constructed. There will be a total of 86 subjects in this three-part trial, 44 subjects in 6 cohorts will receive rezafungin or placebo via SC injection in Part 1/SAD, 32 subjects in 4 cohorts will receive rezafungin or placebo via SC injection in Part 2/MAD, and 10 subjects will receive rezafungin via both SC and IV injections in Part 3/BA. The number of subjects was selected to allow sufficient evaluation of safety, tolerability, and PK of the various dose regimens, and to be consistent with standards of practice for Phase 1 trials.

## 5. GENERAL STATISTICAL CONSIDERATIONS

### 5.1. General Principles

Safety and PK data will be summarized by Dose Group, following the order shown in Section 3.3. Summary statistics for continuous data will include the mean, standard deviation (SD), median, minimum value (min), and maximum value (max). Summary statistics for discrete data will include counts and percent and may include confidence intervals (CIs) for the percent. When 95% CIs are given for a percent, Wilson Score CIs will be used. All subjects that are randomized will be included in the summaries of demographics, the Safety Population will be used for summaries of safety endpoints, and PK Population or PK Analysis Subset will be used for summaries of PK endpoints.

Generally, for summaries of safety endpoints, denominators will use the number of subjects in the Safety Population. Denominators for study time points of solicited local reactogenicity symptoms, clinical laboratory results, VS, and ECG results will use the number of subjects with an observed result at the time point for the parameter or symptom. Denominators for the conceptual “Max Severity Post-Baseline” time point for solicited local reactogenicity symptoms, clinical laboratory results, VS, and ECG results will use the number of subjects with an observed result for the parameter obtained post-dose.

The sort order of the listings as is indicated in the Implementation Note for each listing shell (Appendix 3).

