For women of child-bearing potential, a serum pregnancy test will be done at screening and must be negative for eligibility into this trial. A serum pregnancy test will be done on Day -1, which must be reported as negative before dosing. A serum pregnancy test will be repeated at the final trial visit. Perform FSH test in postmenopausal females only, prior to randomization.

Safety Laboratory Tests

The following laboratory tests will be performed as specified in [Appendix A](#). Subjects will be fasting. This means no food or drink (other than water) for at least 8 hours before sampling.

- Hematology: complete blood count (CBC) with differential (red blood cell count, total and differential white blood cell counts, hemoglobin, hematocrit, and platelet count),
- Coagulation; (activated partial thromboplastin time [APTT], prothrombin time [PT}, and international normalized ratio [INR]),

- All subjects must undergo clinical chemistry testing (albumin, glucose, blood urea nitrogen or urea, potassium, calcium, sodium, chloride, total protein, creatinine, total carbon dioxide (CO₂), creatine phosphokinase (CK), phosphorus, alkaline phosphatase, aspartate aminotransferase (AST), alanine aminotransferase (ALT), total bilirubin, direct bilirubin at Screening and Baseline to assess protocol eligibility. Clinical chemistry tests will be performed thereafter as specified in the [Schedule of Assessments and Procedures Appendix A](#). Subjects must fast a minimum of 8 hours before blood collection for a clinical chemistry panel.
- Dipstick urinalysis: protein, blood, and glucose must be negative or trace (complete urinalysis to be performed if dipstick urinalysis is positive for blood). Menstruating females failing inclusion criteria due to a positive result may be retested following cessation of menses. Do not exclude subjects with >5 red blood cells/high power field if menstruating.

Laboratory values will be entered in the Clinical Labs eCRF.

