Platelets Decreased – 10 ³ /mm ³	120 – 149	100 – 119	<100
Hematocrit (Male) - %	33.0 -36.1	29.8 - 32.9	< 29.8
Hematocrit (Female) - %	29.5 - 32.6	26.0 – 29.4	< 26.0
RBC (Male) – x 10 ⁶ /uL	3.9 - 4.1	3.4 - 3.8	< 3.4
RBC (Female) – x 10 ⁶ /uL	3.5 - 3.7	3.0 - 3.4	< 3.0
Lymphocytes - cell/mm ³ decrease	600- 799	500 – 599	< 500
Monocytes – cell/mm ³ increase	1001-2000	2001-3000	>3000
Eosinophils - cell/mm ³ increase	871 - 950	951 - 1700	>1700
Basophils - cell/mm ³ increase	101 - 300	301 - 800	> 800
PT (prothrombin time) – seconds	11.6-12.6	12.7-13.7	>13.7
PT INR (Prothrombin INR)	1.2-1.4	1.5-1.9	2.0 or higher
PTT (partial thromboplastin time) –seconds	30.1-36.8	36.9-43.6	>43.6
Urine			
Protein	1+	2+	>2+
Glucose	1+	2+	>2+
Blood (microscopic) - red blood cells per high power field (rbc/hpf)**	3-10*	11-50*	>50 and/or gross blood**

Laboratory Adverse Events*	Mild	Moderate	Severe
	(Grade 1)	(Grade 2)	(Grade 3)
*Abnormal laboratory values, performed as part of hematology, chemistry panel, or urinalysis but not listed in Appendix B , will be evaluated by the study clinicians, recorded in the source document and, if clinically significant, considered AEs and graded according to the criterion described in Section 8.1 .

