## 7.6. Clinical Laboratory Evaluations

If the time of sample collection for clinical laboratory evaluations was prior to 23DEC2019, then grading will follow toxicity grade criteria from protocol v3.0. If the time of sample collection was on or after 23DEC2019, then grading will follow toxicity grade criteria from protocol v4.0. Note that toxicity ranges from protocol v4.0 through v6.0 were identical.

- CHEM: Total cholesterol, low-density lipoprotein cholesterol, high-density lipoprotein cholesterol, and triglycerides were removed from clinical lab collection after protocol v3.0.
- COAG: Prothrombin time and activated PTT toxicity ranges were updated after protocol v3.0.
- UA: Blood in urine (microscopic) toxicity ranges were updated after protocol v3.0.

All screening and safety laboratory results will be listed in [Listing 11](#) (CHEM), [Listing 12](#) (HEM), [Listing 13](#) (COAG), [Listing 14](#) (UA), [Listing 15](#) (serology), [Listing 16](#) (urine toxicity), and [Listing 17](#) (pregnancy test). Abnormal laboratory results (laboratory results outside of the normal range on time of collection) will be listed in [Table 16](#) (CHEM), [Table 17](#) (HEM), [Table 18](#) (COAG), and [Table 19](#) (UA).

Laboratory results will be summarized in tables and figures:

- Tabularly, by parameter, Dose Group, time point, and toxicity grade (including maximum severity post-baseline). Summaries will be presented in [Table 20](#) (CHEM), [Table 22](#) (HEM), [Table 24](#) (COAG), and [Table 26](#) (UA). When calculating the proportions of subjects with a laboratory toxicity, each subject will only be counted once per toxicity grade and any repetitions of laboratory toxicities within a subject will be ignored, and the event will be reported according to the worst severity recorded. Parameters with no specified toxicity ranges listed in protocol will be excluded from this summary.
- Tabularly, by summary statistics for change from baseline, reported by parameter, Dose Group, and time point. Summaries will be presented in [Table 21](#) (CHEM), [Table 23](#) (HEM), and [Table 25](#) (COAG).
- Graphically, using box plots of change from baseline by parameter, Dose Group, and time point.
  - CHEM: Beginning at [Figure 19](#) and continuing through [Figure 35](#).
  - HEM: Beginning at [Figure 36](#) and continuing through [Figure 45](#).
  - COAG: [Figure 46](#), [Figure 47](#), and [Figure 48](#).

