The following laboratory parameters will be presented (in order):

- Chemistry (CHEM): sodium, potassium, calcium, phosphorus, chloride, total carbon dioxide, glucose, blood urea nitrogen, creatinine, total cholesterol, low-density lipoprotein cholesterol, high-density lipoprotein cholesterol, triglycerides, total protein, albumin, aspartate aminotransferase (AST), alanine aminotransferase (ALT), alkaline phosphatase, total bilirubin, direct bilirubin, creatine phosphokinase. Total cholesterol, low-density lipoprotein cholesterol, high-density lipoprotein cholesterol, and triglycerides parameters were removed after Protocol v3.0. Only Cohort 1 subjects have results for the specified parameters. Due to limited number of subjects with available results, total cholesterol, low-density lipoprotein cholesterol, high-density lipoprotein cholesterol, and triglycerides will only be presented in [Table 21](#) and [Listing 11](#) and will be excluded from the change from baseline figures.
- Hematology (HEM): hemoglobin, hematocrit, RBC count, WBC count, neutrophil count, lymphocyte count, monocyte count, eosinophil count, basophil count, platelet count.
- Coagulation (COAG): prothrombin time, activated PTT, INR
- Urinalysis (UA): protein, glucose, occult blood.

By protocol, microscopic evaluation of urine or complete urinalysis is only performed if dipstick urinalysis is positive for blood. If complete UA or microscopic results were obtained in the absence of an abnormal dipstick result (or without dipstick tests being done), results of the complete UA or microscopy will still be summarized. Results determined using both methods will be listed. In tables, dipstick results will be presented prior to complete UA or microscopy results.

Laboratory parameters that have grading criteria for both decreases (result lower than normal range) and increases (result higher than normal range) will be summarized separately by direction of change. For example, sodium will be summarized separately as “Sodium, Decrease” and “Sodium, Increase.”

In tables summarizing toxicity grading, maximum severity observed after dosing will be summarized (max severity post-baseline, including unscheduled visits) for each parameter. Results of maximum severity for “Any Parameter” will be included for all clinical laboratory results. For “Any Parameter” results, the maximum severity across all laboratory parameters in the respective category is summarized by time point.

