**14.3.5.4 Urinalysis Results****Table 26: Urinalysis Toxicity Grade by Parameter, Severity, Dose Group, and Time Point**

[Implementation Note: Severity will be graded based on toxicity criteria in protocol. If there is not at least 1 Mild, Moderate, or Severe Event for Max Severity Post-Baseline, then only the Max Severity Post-Baseline row will be shown for the parameter. Toxicities representing an increase in the laboratory result will be summarized separately from decreases.]

This table will repeat Table 20 for Urinalysis parameters.
--

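### Table 26 counts microscopic urine blood only over subjects who had microscopy, which mainly follows a positive dipstick, so a graded case can print at too high a percentage

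*SAP*

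**What the plan says.** Five provisions combine.

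- **Denominator.** SAP 5.1 says that laboratory denominators at a time point "will use the number of subjects with an observed result at the time point for the parameter or symptom". For the Max Severity Post-Baseline row they "will use the number of subjects with an observed result for the parameter obtained post-dose".
- **Table layout.** The Table 26 shell says "This table will repeat Table 20 for Urinalysis parameters". The Table 20 footnote also defines N by whether that laboratory result was assessed.
- **When microscopy is done.** SAP 7.6: "By protocol, microscopic evaluation of urine or complete urinalysis is only performed if dipstick urinalysis is positive for blood". Protocol 7.2.1 has the same trigger: "complete urinalysis to be performed if dipstick urinalysis is positive for blood". If microscopy was done without an abnormal dipstick, SAP 7.6 says that "results of the complete UA or microscopy will still be summarized".
- **What is graded.** The urine section of protocol Appendix B grades protein, glucose and "Blood (microscopic) - red blood cells per high power field". It gives no grade for dipstick blood.
- **What is left out.** SAP 7.6 says of the toxicity tables: "Parameters with no specified toxicity ranges listed in protocol will be excluded from this summary". SAP 5.5 plans no imputation.

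Neither document gives microscopic blood a wider denominator or says that a negative dipstick counts as no toxicity in Table 26.

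**The concern.** Using observed results as the denominator is sensible when a result is absent because a sample was missed. Here a result is usually absent because the screening test was negative. Those subjects were tested and gave no reason to look further, yet they leave the denominator. N is therefore selected by a screen for the outcome being counted.

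Two things follow. The percentage of subjects with graded hematuria can be too high. It is also hard to compare between baseline and post-dose, between rezafungin and placebo, or with the protein and glucose rows, because each figure rests on a differently selected subset. Safety is a primary objective and only SAD Cohorts 1 and 2 are analysed, so each subject moves a percentage a long way.

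**Working it through.** The plan states no percentage on this point, so there is no figure to reproduce.

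**Inputs.** Protocol Table 1 gives 3 active and 1 placebo in Cohort 1, and 6 active and 2 placebo in Cohort 2. The SAP 3.3.1 groups are then 1 mg = 3, 10 mg = 6, any dose = 3 + 6 = 9, and pooled placebo = 1 + 2 = 3. Actual counts are not given; I assume the cohorts filled as planned and everyone had a urinalysis at the visit. In Appendix B, microscopic blood is mild at 3-10, moderate at 11-50 and severe above 50 rbc/hpf.

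**Formula.** Let k be the subjects with a graded result, m those with microscopy and n those with any urinalysis. The SAP rule prints k/m. The all-tested figure is k/n. For k of at least 1 the ratio is (k/m)/(k/n) = n/m. This exceeds 1 whenever m is below n and equals 1 when m = n.

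**One graded case (k = 1), for example 15 rbc/hpf, moderate:**

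| Group | n | All-tested 1/n | SAP rule, m = 1 | m = 2 | m = 3 |
|---|---|---|---|---|---|
| 1 mg | 3 | 33% | 100% | 50% | 33% |
| 10 mg | 6 | 17% | 100% | 50% | 33% |
| Any dose | 9 | 11% | 100% | 50% | 33% |
| Placebo | 3 | 33% | 100% | 50% | 33% |

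In the 10 mg group, m = 4, 5 and 6 give 25%, 20% and 17%. If nobody is graded (k = 0) and m is at least 1, both methods give 0%.

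**Comparison between groups (hypothetical).** Suppose one graded case in each group, with m = 1 on 10 mg and m = 2 on placebo. The table prints 100% against 50%. Over all tested, the figures are 1/6 = 17% against 1/3 = 33%, so the order reverses.

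**Consistency within the table.** SAP 7.6 also asks for an Any Parameter row, the maximum severity across the urinalysis category. Protein and glucose come from the scheduled dipstick, so N there would be about 6 in the 10 mg group. With no other graded finding, one case gives 1/6 = 17% in that row and 1/1 = 100% in the microscopic blood row when m = 1.

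**How often m would be 1.** The documents give no dipstick-positive rate. Assuming independent rates p of 5%, 10% and 20%, the chance of exactly one microscopy given at least one is np(1-p)^(n-1) / [1-(1-p)^n]:

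| n | p = 5% | p = 10% | p = 20% |
|---|---|---|---|
| 3 | 95% | 90% | 79% |
| 6 | 88% | 76% | 53% |
| 9 | 81% | 63% | 35% |

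This concerns how many subjects have microscopy, not whether the result is graded.

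**The case against.** The strongest counter-reading is that the parameter is occult blood, measured by two methods. SAP 7.6 lists it as a single urinalysis parameter, and the Table 19 shell shows a negative occult-blood dipstick entry. On that view a dipstick-negative subject has an observed result for the parameter and already belongs in N. The reading is possible but strained. SAP 7.6 places dipstick results ahead of microscopy results in tables, which points to separate rows by method. It describes the blood toxicity ranges as microscopic, and Appendix B grades nothing else for urine blood. A dipstick row carrying the full N would also conflict with the rule that drops ungraded parameters. If a combined N was meant, the SAP still needs to say so.

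Several mitigating points stand. N and n are printed beside each percentage, so a reader would see N = 1, though nothing would say that a positive dipstick selected that subject. The Any Parameter row has a sounder denominator. Table 19 and Listing 14 show results by subject. Microscopy done without the trigger would enlarge N, though only irregularly.

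A reader might infer that any single case prints as 100%. The documents do not support that. It happens only when every subject with microscopy in the row has that grade: one graded of two prints 50%, and a single microscopy below 3 rbc/hpf prints 0/1.

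**Conclusion.** The point holds as a conditional overstatement. When at least one microscopic blood result is graded and not all tested subjects had microscopy, the stated rule inflates the percentage by n/m. At planned size, one case on 10 mg prints as 100% (m = 1) or 50% (m = 2) instead of 17%.

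This rests on planned group sizes, on separate rows by method, and on taking a negative dipstick as no graded hematuria. SAP 7.6 applies protocol v3.0 ranges to samples before 23DEC2019. Those ranges are not in the documents, but they affect the grade and not the denominator rule.

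A reader might go further and infer that the trial's safety conclusions or stopping decisions are distorted. The documents do not support that. The halting rules in protocol 8.7 do not use Table 26 percentages, the analyses are descriptive, and the Table 26 shell has no confidence intervals. It is one row, worth correcting because the correction is cheap.

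**What to change.** Add to SAP 5.1, SAP 7.6 and the Table 26 note:

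- For microscopic blood, at each time point and for Max Severity Post-Baseline, N is the number of subjects with a dipstick-blood or microscopy result in that period.
- A dipstick that did not trigger reflex microscopy counts as no graded hematuria. If microscopy was done anyway, its result is used.
- State how trace dipsticks are classed. Protocol 7.2.1 accepts negative or trace, but neither document ties trace to fewer than 3 rbc/hpf, so this should be an explicit choice.
- A positive dipstick without microscopy stays missing.
- Footnote the number of subjects who had microscopy in each group and row.

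The cost is a short SAP addition and one derivation line, using data already collected. The drawback is small: a negative dipstick is accepted as no graded hematuria without microscopic confirmation. This should be written as a classification rule so that it does not conflict with the no-imputation statement in SAP 5.5. If the team prefers the conditional denominator, the minimum is to label the row as restricted to subjects with microscopy.
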